10.3 Appendix 3: Clinical laboratory tests

10.3.1 Clinically notable laboratory values and vital signs

Clinically significant abnormal laboratory values or test results must be identified through a review of values outside of normal ranges/clinically notable ranges, significant changes from baseline or the previous visit.

Table 10-1 Clinically notable laboratory values

Parameter	Conventional Alert Value	Conventional Units	SI Alert Value	SI Units
Hematology				
Red Blood Cell Count	>50% increase, >30% decrease	$\times 10^6/\mu\text{L}$	>50% increase, >30% decrease	$\times 10^{12}/\text{L}$
Hemoglobin	>50% increase, 30% decrease, or any value <7	g/dL	>50% increase, >30% decrease, or any value <70	g/L
Hematocrit	>50% increase, >30% decrease	%	>50% increase, >30% decrease	L/L
White Blood Cell Count	>50% increase, >50% decrease	$\times 10^3/\mu\text{L}$	>50% increase, >50% decrease	$\times 10^9/\text{L}$
Platelet Count	>75% increase, >50% decrease	$\times 10^3/\mu\text{L}$	>75% increase, >50% decrease	$\times 10^9/\text{L}$
Chemistry				
BUN	>50% increase	mg/dL	>50% increase	mmol/L
Creatinine	>50% increase	mg/dL	>50% increase	$\mu\text{mol}/\text{L}$
Albumin	<2	g/dL	<20	g/L
Glucose	>50% increase, >50% decrease, or any value <60	mg/dL	>50% increase, >50% decrease, or any value <3.3	mmol/L
Total Bilirubin	>100% increase	mg/dL	>100% increase	$\mu\text{mol}/\text{L}$
Creatine phosphokinase (CPK)	>300% increase	U/L	>300% increase	U/L
AST (SGOT)	>150% increase	U/L	>150% increase	U/L
ALT (SGPT)	>150% increase	U/L	>150% increase	U/L
Alkaline phosphatase	>100% increase	U/L	>100% increase	U/L
Sodium	>5% increase, or any value >150	mEq/L	>5% increase, or any value >150	mmol/L
Potassium	>20% increase, >20%	mEq/L	>20% increase, >20%	mmol/L

Parameter	Conventional Alert Value	Conventional Units	SI Alert Value	SI Units
	decrease, or any value >5.3		decrease, or any value >5.3	
Chloride	>10% increase, >10% decrease	mEq/L	>10% increase, >10% decrease	mmol/L
Calcium	>10% increase, >10% decrease	mg/dL	>10% increase, >10% decrease	mmol/L
Uric Acid	>50% increase	mg/dL	>50% increase	mmol/L

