10.5 Appendix 5: Liver safety monitoring

To ensure participant safety and enhance reliability in determining the hepatotoxic potential of an investigational drug, a standardized process for identification, monitoring and evaluation of liver events has to be followed.

Please refer to [Table 10-2](#) in Appendix 5 for complete definitions of liver laboratory triggers.

Once a participant is exposed to study treatment, every liver event defined in [Table 10-2](#) should be followed-up by the investigator or designated personnel at the trial site, as summarized below. Additional details on actions required in case of liver events are outlined in [Table 10-3](#) and [Table 10-4](#). Repeat liver chemistry tests (i.e. ALT, AST, TBL, PT/INR, ALP and G-GT) to confirm elevation.

If a liver event is subsequently reported, any local liver chemistry tests previously conducted that are associated with this event should have results recorded on the appropriate eCRF.

If the initial elevation is confirmed, close observation of the participant will be initiated, including consideration of treatment interruption if deemed appropriate.

Hospitalization of the participant if appropriate.

Causality assessment of the liver event.

Thorough follow-up of the liver event should include:

These investigations can include based on investigator's discretion: serology tests, imaging and pathology assessments, hepatologist's consultancy; obtaining more detailed history of symptoms and prior or concurrent diseases, history of concomitant drug use, exclusion of underlying liver disease.

Obtaining a more detailed history of symptoms and prior or concurrent diseases.

Obtaining a history of concomitant drug use (including nonprescription medications and herbal and dietary supplement preparations), alcohol use, recreational drug use, and special diets.

Exclusion of underlying liver disease.

Imaging such as abdominal US, CT or Magnetic Resonance Imaging (MRI) , as appropriate.

Obtaining a history of exposure to environmental chemical agents.

Considering gastroenterology or hepatology consultations.

All follow-up information and procedures performed must be recorded as appropriate in the eCRF.

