10.5.1 Liver event and laboratory trigger definitions & follow-up requirements

Table 10-2 Liver event and laboratory trigger definitions

	Definition/ threshold
If ALT or AST normal at baseline:	
Liver laboratory triggers	$3 \times \text{ULN} < \text{ALT or AST} \leq 5 \times \text{ULN}$ $\text{TBL} > \text{ULN}^*$

Liver events	ALT or AST > 5 × ULN ALP > 2 × ULN (in the absence of known bone pathology) Total bilirubin > 3 × ULN (in the absence of known Gilbert syndrome) ALT or AST > 3 × ULN AND (TBL > 2 × ULN OR INR > 1.5) Potential Hy's Law cases (defined as ALT or AST > 3 × ULN and Total bilirubin > 2 × ULN [mainly conjugated fraction] without notable increase in ALP to > 2 × ULN) Any clinical event of jaundice (or equivalent term) ALT or AST > 3 × ULN accompanied by (general) malaise, fatigue, abdominal pain, nausea, or vomiting, or rash with eosinophilia Any adverse event potentially indicative of a liver toxicity
If ALT or AST elevated at baseline:	
Liver laboratory triggers	ALT or AST > 2 × baseline or > 200 U/L (whichever occurs first) TBL > ULN*
Liver events	ALT or AST > 3 × baseline or > 300 U/L (whichever occurs first) (ALT or AST > 2 × baseline or > 200 U/L [whichever occurs first]) AND (TBL > 2 × ULN OR INR > 1.5) ALT or AST > 5 × ULN ALP > 2 × ULN (in the absence of known bone pathology) Total bilirubin > 3 × ULN (in the absence of known Gilbert syndrome) Potential Hy's Law cases (defined as ALT or AST > 3 × ULN and Total bilirubin > 2 × ULN [mainly conjugated fraction] without notable increase in ALP to > 2 × ULN) Any clinical event of jaundice (or equivalent term) (ALT or AST > 2 × baseline or > 200 U/L [whichever occurs first]) accompanied by (general) malaise, fatigue, abdominal pain, nausea, or vomiting, or rash with eosinophilia Any adverse event potentially indicative of a liver toxicity

* Fractionate bilirubin, evaluate for cholestatic liver injury (ALP) or alternative causes of bilirubin elevation. Treat alternative causes according to local institutional guidelines

Table 10-3 Follow-up requirements for liver laboratory triggers - ALT, AST, TBL

ALT	TBL	Liver Symptoms	Action
ALT increase without bilirubin increase:			
If normal at baseline: ALT > 3 × ULN	Normal For participants with Gilbert's syndrome: No change in baseline TBL	None	
 Measure ALT, AST, ALP, GGT, TBIL, INR, albumin, CK, and Glutamate dehydrogenase (GLDH) in 48-72 hours. Follow-up for symptoms.

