10.6 Appendix 6: Renal safety monitoring

Once a participant is exposed to study treatment, the following two categories of abnormal renal laboratory alert values should be assessed during the study period:

Serum creatinine increase $\geq 25\%$ compared to baseline during normal hydration status

Any one of the following:

Urine protein-creatinine ratio (PCR) $\geq 1\text{g/g}$ or $\geq 100\text{ mg/mmol}$, OR

New onset dipstick proteinuria $\geq 3+$, OR

New onset dipstick hematuria $\geq 3+$ (after excluding menstruation, Urinary tract infection (UTI), extreme exercise, or trauma)

Abnormal renal event findings must be confirmed within 24-48 hours after the first assessment.

Once a participant is exposed to study treatment, renal laboratory alerts or renal safety events should be monitored and followed-up by the Investigator or designated trial staff as summarized in [Table 10-5](#).

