Summary statistics for all laboratory data will be provided by treatment and visit/time. Shift tables using the low/normal/high/ (low and high) classification may be used, as appropriate, to compare baseline to the worst value. Where normal ranges are available, abnormalities in laboratory data will be listed by treatment group, participant, and visit/time.

Graphical displays of selected safety parameters (e.g. hematological parameters, thyroid and reproductive hormone levels) over time will be provided by treatment group.

For laboratory parameters which are lower or greater than the limit of quantification, the number and percentage of values below the lower limit of quantification (LLOQ) and above the upper limit of quantification (ULOQ) will be presented for categorical variables. For numerical presentation, the values less than LLOQ will be imputed as a value of $0.5 \times \text{LLOQ}$ and the values greater than ULOQ will be imputed as a value of $1.5 \times \text{ULOQ}$.

The frequency and percentage of participants with clinically significant abnormal laboratory values shown in [Table 2-2](#) will also be provided.

Table 2-2 **Clinically notable laboratory values**

Parameter	Conventional Alert Value	Conventional Units	SI Alert Value	SI Units
Hematology				
Red Blood Cell Count	>50% increase, >30% decrease	$\times 10^6/\mu\text{L}$	>50% increase, >30% decrease	$\times 10^{12}/\text{L}$
Hemoglobin	>50% increase, 30% decrease, or any value <7	g/dL	>50% increase, >30% decrease, or any value <70	g/L
Hematocrit	>50% increase, >30% decrease	%	>50% increase, >30% decrease	L/L
White Blood Cell Count	>50% increase, >50% decrease	$\times 10^3/\mu\text{L}$	>50% increase, >50% decrease	$\times 10^9/\text{L}$
Platelet Count	>75% increase, >50% decrease	$\times 10^3/\mu\text{L}$	>75% increase, >50% decrease	$\times 10^9/\text{L}$
Chemistry				
BUN	>50% increase	mg/dL	>50% increase	mmol/L
Creatinine	>50% increase	mg/dL	>50% increase	$\mu\text{mol}/\text{L}$
Albumin	<2	g/dL	<20	g/L
Glucose	>50% increase, >50% decrease, or any value <60	mg/dL	>50% increase, >50% decrease, or any value <3.3	mmol/L
Total Bilirubin	>100% increase	mg/dL	>100% increase	$\mu\text{mol}/\text{L}$
Creatine phosphokinase (CPK)	>300% increase	U/L	>300% increase	U/L
AST (SGOT)	>150% increase	U/L	>150% increase	U/L
ALT (SGPT)	>150% increase	U/L	>150% increase	U/L
Alkaline phosphatase	>100% increase	U/L	>100% increase	U/L

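### Laboratory-defined liver events in protocol Table 10-2, including potential Hy's Law, have no planned by-arm count, and the percent-change count in SAP Table 2-2 can miss them when baseline liver tests are raised

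*Protocol*

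**What the plan says.** **The liver definitions.** Protocol 10.5 states that "a standardized process for identification, monitoring and evaluation of liver events has to be followed". Table 10-2 in 10.5.1 then defines liver events, mostly as multiples of ULN and partly as combinations. One is "ALT or AST > 3 × ULN AND (TBL > 2 × ULN OR INR > 1.5"). Another is "Potential Hy's Law cases (defined as ALT or AST > 3 × ULN and Total bilirubin > 2 × ULN [mainly conjugated fraction"], with the further condition "without notable increase in ALP to > 2 × ULN". There are also single-test events: ALT or AST above 5 x ULN, bilirubin above 3 x ULN, and ALP above 2 x ULN. A separate branch covers ALT or AST elevated at baseline.

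**The notable-value table.** Protocol 10.3.1 opens with the rule "Clinically significant abnormal laboratory values or test results must be identified through a review of values outside of normal ranges/clinically notable ranges". Its Table 10-1 sets ALT and AST at ">150% increase" and total bilirubin and ALP at a rise of more than 100%. These rows have no ULN limit, and the table has no INR row. The same opening sentence goes on to mention change from baseline or from the previous visit and does not choose between them.

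**The count.** SAP 2.6.1 commits to this: "The frequency and percentage of participants with clinically significant abnormal laboratory values shown in" Table 2-2, whose liver rows are those of Table 10-1. SAP tables are by treatment group. SAP 2.6.1 also plans treatment-emergent AE tables by system organ class and preferred term, by-visit laboratory summaries, and a listing of abnormal values by arm and participant. Shift tables are optional.

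**What is absent.** Liver is not among the four adverse events of special interest counted in SAP 2.6.1. SAP section 4 drops the protocol's SMQ summary. SAP 2.7 refers all safety analyses back to 2.6.

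**The concern.** Safety laboratory parameters belong to the secondary endpoint, and protocol 10.5 exists to help determine hepatotoxic potential. A single-analyte, percent-change rule cannot represent a combined criterion, and it is least sensitive in participants who start with raised values. Such participants are plausible here. A bilirubin of 2.0 to 5.9 mg/dL scores 2 SOFA points (Table 8-2), which is enough by itself to reach the non-renal SOFA threshold for entry. With about 15 participants on TIN816 and 5 on placebo, one potential Hy's Law case matters, and the planned count of notable values could show zero for it.

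**Working it through.** The documents give no figure on this point, so the check compares thresholds.

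**Inputs.** From Table 10-2, potential Hy's Law needs ALT or AST > 3 x ULN, bilirubin > 2 x ULN (mainly conjugated) and ALP not > 2 x ULN. From Table 2-2, a flag needs ALT or AST > 2.5 x the reference value (a rise above 150%), or bilirubin or ALP > 2 x the reference value (a rise above 100%).

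**Rule.** A value just over k x ULN escapes a row that needs m x baseline when k x ULN < m x baseline, that is, when baseline > (k/m) x ULN.

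| Table 10-2 limit | Table 2-2 multiple | Baseline needed to escape |
|---|---|---|
| ALT/AST > 3 x ULN | 2.5 | > 3/2.5 = 1.2 x ULN |
| Bilirubin > 2 x ULN | 2 | > 2/2 = 1.0 x ULN |
| ALT/AST > 5 x ULN | 2.5 | > 5/2.5 = 2.0 x ULN |
| Bilirubin > 3 x ULN | 2 | > 3/2 = 1.5 x ULN |
| ALP > 2 x ULN | 2 | > 2/2 = 1.0 x ULN |

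For potential Hy's Law the first two rows must both hold. If ALT and AST both exceed 3 x ULN, both need the raised baseline. The peaks must also stay inside the unflagged windows:

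- Baseline ALT 1.5, 2.0 or 3.0 x ULN: peak above 3 and up to 3.75, 5.0 or 7.5 x ULN.
- Baseline bilirubin 1.2, 1.5 or 2.0 x ULN: peak above 2 and up to 2.4, 3.0 or 4.0 x ULN.

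**Worked case.** Assume ULN 40 U/L for ALT and 1.2 mg/dL for bilirubin, with AST and ALP not meeting their rows.

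- ALT 60 to 130 U/L: 130 > 3 x 40 = 120, but 130/60 - 1 = +117%. The row needs more than 2.5 x 60 = 150.
- Bilirubin 1.5 to 2.6 mg/dL, mainly conjugated: 2.6 > 2 x 1.2 = 2.4, but 2.6/1.5 - 1 = +73%. The row needs more than 2 x 1.5 = 3.0.
- Result: one potential Hy's Law case and no Table 2-2 liver flag.

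**INR combination.** In the elevated-baseline branch, ALT above 2 x baseline with INR above 1.5 is a liver event. The same ALT path (130/60 = 2.17 x baseline) with such an INR qualifies without any bilirubin rise. The ALT row is not met, and INR has no row.

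**Normal baselines.** With transaminase and bilirubin at or below ULN, a simulation of 200,000 potential Hy's Law cases found none missed. If only transaminase is raised, the bilirubin row catches the case: ALT 1.5 to 3.2 and bilirubin 0.8 to 2.2 x ULN gives bilirubin +175%.

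**Entry.** Exclusion criterion 16 places its enzyme limit for ALT and ALP at 3 x ULN and gives no numeric limit of its own for AST or bilirubin. A bilirubin of 2.0 mg/dL (1.67 x the assumed ULN) is not flagged until it passes 4.0, although the > 3 x ULN event starts above 3.6.

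**Reference value.** If an increase means against the previous visit, a normal-baseline case can also escape. ALT 1 to 2 to 3.2 x ULN is +100% then +60%; bilirubin 1 to 1.6 to 2.2 x ULN is +60% then +38%.

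**The case against.** The sponsor has a reasonable reply. All abnormal results are assessed against the AE criteria (protocol 8.4.4 and 8.6.1), every Table 10-2 event requires follow-up and a causality assessment, and Table 10-4 has the AE recorded for isolated bilirubin above 3 x ULN. Jaundice is an AE by nature. In a descriptive study of about 20 participants, a listing of every out-of-range value is a workable way to find a rare case. All of this stands. It does not supply the count: a laboratory-only case becomes an AE only if symptomatic, judged clinically significant or treated, and the AE tables would not identify it as a Table 10-2 event.

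A reader might infer more than the documents support:

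- **That liver events have no by-arm count of any kind.** Reported liver AEs are counted by arm by system organ class and preferred term.
- **That a case would vanish from the report.** It would be in the abnormal-value listing.
- **That Tables 10-1 and 10-2 contradict each other.** One supports review of notable values and the other triggers site follow-up. The sentence above Table 10-1 also covers any value outside the normal range.
- **That creatinine carries conflicting alert values.** Protocol 10.6 alerts at 25%, and Table 10-5 grades it at 25-49% and 50% or more; the upper tier is close to the more-than-50% row of Table 10-1. This is largely a graded scheme.

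Nor is there a case for forcing one alert value per analyte, since that would mean choosing a clinical threshold.

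**Conclusion.** The point holds in a limited form. The SAP's only committed threshold-based laboratory count cannot represent the combined liver events that the protocol defines, and the public text plans no by-arm tabulation of laboratory-defined Table 10-2 events. Measured against baseline, the Hy's Law miss is confined to participants with transaminase above 1.2 x ULN and bilirubin above 1.0 x ULN at baseline, and to peaks within the windows shown. Single-test events can be missed from one raised analyte alone.

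The documents do not say how often these baselines occur, so no expected number of missed cases can be given. The worked case rests on assumed ULNs; the multiples do not. SAP sections between 2.7 and 2.11 are not visible, so a liver table there cannot be fully excluded, although 2.7 points to 2.6. This is a worthwhile, inexpensive improvement, not a flaw that threatens the study.

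**What to change.** In SAP 2.6.1, add n (%) of participants by arm meeting each Table 10-2 liver event exactly as the protocol defines it: ALT/AST with bilirubin or INR, potential Hy's Law, and each single-test event. Use scheduled and unscheduled post-dose results; SAP 2.1.1 already admits unscheduled values to summaries of notable abnormalities. Split by normal or elevated baseline: ALT/AST status as in Table 10-2, and the analyte's own baseline for the bilirubin and ALP events. List the individual cases. Separately, state in Table 2-2 whether an increase is measured from baseline or from the previous visit. No clinical threshold changes.

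The cost is SAP wording, one extra table and a short listing from data already planned for collection. The drawback is that some counted events will reflect pre-existing sepsis cholestasis; the baseline split makes that visible.

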10.4 Appendix 4: Participant Engagement

The following participant engagement initiatives are included in this study and will be provided, as available, for distribution to study participants at the time points indicated. If compliance is impacted by cultural norms or local laws and regulations, sites may discuss modifications to these requirements with Novartis.

Thank You letter

Plain language trial summary - after Clinical study report (CSR) publication.

10.5 Appendix 5: Liver safety monitoring

To ensure participant safety and enhance reliability in determining the hepatotoxic potential of an investigational drug, a standardized process for identification, monitoring and evaluation of liver events has to be followed.

Please refer to [Table 10-2](#) in Appendix 5 for complete definitions of liver laboratory triggers.

Once a participant is exposed to study treatment, every liver event defined in [Table 10-2](#) should be followed-up by the investigator or designated personnel at the trial site, as summarized below. Additional details on actions required in case of liver events are outlined in [Table 10-3](#) and [Table 10-4](#). Repeat liver chemistry tests (i.e. ALT, AST, TBL, PT/INR, ALP and G-GT) to confirm elevation.

If a liver event is subsequently reported, any local liver chemistry tests previously conducted that are associated with this event should have results recorded on the appropriate eCRF.

If the initial elevation is confirmed, close observation of the participant will be initiated, including consideration of treatment interruption if deemed appropriate.

Hospitalization of the participant if appropriate.

Causality assessment of the liver event.

Thorough follow-up of the liver event should include:

These investigations can include based on investigator's discretion: serology tests, imaging and pathology assessments, hepatologist's consultancy; obtaining more detailed history of symptoms and prior or concurrent diseases, history of concomitant drug use, exclusion of underlying liver disease.

Obtaining a more detailed history of symptoms and prior or concurrent diseases.

Obtaining a history of concomitant drug use (including nonprescription medications and herbal and dietary supplement preparations), alcohol use, recreational drug use, and special diets.

Exclusion of underlying liver disease.

Imaging such as abdominal US, CT or Magnetic Resonance Imaging (MRI) , as appropriate.

Obtaining a history of exposure to environmental chemical agents.

Considering gastroenterology or hepatology consultations.

All follow-up information and procedures performed must be recorded as appropriate in the eCRF.

10.5.1 Liver event and laboratory trigger definitions & follow-up requirements

Table 10-2 Liver event and laboratory trigger definitions

	Definition/ threshold
If ALT or AST normal at baseline:	
Liver laboratory triggers	$3 \times \text{ULN} < \text{ALT or AST} \leq 5 \times \text{ULN}$ $\text{TBL} > \text{ULN}^*$

Liver events	ALT or AST > 5 × ULN ALP > 2 × ULN (in the absence of known bone pathology) Total bilirubin > 3 × ULN (in the absence of known Gilbert syndrome) ALT or AST > 3 × ULN AND (TBL > 2 × ULN OR INR > 1.5) Potential Hy's Law cases (defined as ALT or AST > 3 × ULN and Total bilirubin > 2 × ULN [mainly conjugated fraction] without notable increase in ALP to > 2 × ULN) Any clinical event of jaundice (or equivalent term) ALT or AST > 3 × ULN accompanied by (general) malaise, fatigue, abdominal pain, nausea, or vomiting, or rash with eosinophilia Any adverse event potentially indicative of a liver toxicity
If ALT or AST elevated at baseline:	
Liver laboratory triggers	ALT or AST > 2 × baseline or > 200 U/L (whichever occurs first) TBL > ULN*
Liver events	ALT or AST > 3 × baseline or > 300 U/L (whichever occurs first) (ALT or AST > 2 × baseline or > 200 U/L [whichever occurs first]) AND (TBL > 2 × ULN OR INR > 1.5) ALT or AST > 5 × ULN ALP > 2 × ULN (in the absence of known bone pathology) Total bilirubin > 3 × ULN (in the absence of known Gilbert syndrome) Potential Hy's Law cases (defined as ALT or AST > 3 × ULN and Total bilirubin > 2 × ULN [mainly conjugated fraction] without notable increase in ALP to > 2 × ULN) Any clinical event of jaundice (or equivalent term) (ALT or AST > 2 × baseline or > 200 U/L [whichever occurs first]) accompanied by (general) malaise, fatigue, abdominal pain, nausea, or vomiting, or rash with eosinophilia Any adverse event potentially indicative of a liver toxicity

* Fractionate bilirubin, evaluate for cholestatic liver injury (ALP) or alternative causes of bilirubin elevation. Treat alternative causes according to local institutional guidelines

Table 10-3 Follow-up requirements for liver laboratory triggers - ALT, AST, TBL

ALT	TBL	Liver Symptoms	Action
ALT increase without bilirubin increase:			
If normal at baseline: ALT > 3 × ULN	Normal For participants with Gilbert's syndrome: No change in baseline TBL	None	
 Measure ALT, AST, ALP, GGT, TBIL, INR, albumin, CK, and Glutamate dehydrogenase (GLDH) in 48-72 hours. Follow-up for symptoms.
If elevated at baseline: ALT > 2 × baseline or > 300 U/L (whichever occurs first)			
If normal at baseline: ALT > 5 × ULN for more than two weeks	Normal For participants with Gilbert's syndrome: No change in baseline TBL	None	
 Measure ALT, AST, ALP, GGT, TBIL, INR, albumin, CK, and GLDH in 48-72 hours. Follow-up for symptoms. Initiate close monitoring and workup for competing etiologies.
If elevated at baseline: ALT > 3 × baseline or > 300 U/L (whichever occurs first) for more than two weeks			
If normal at baseline: ALT > 8 × ULN	Normal	None	
ALT increase with bilirubin increase:			
If normal at baseline: ALT > 3 × ULN	TBL > 2 × ULN (or INR > 1.5) For participants with Gilbert's syndrome: Doubling of direct bilirubin	None	
If elevated at baseline: ALT > 2 × baseline or > 300 U/L (whichever occurs first)			
If normal at baseline: ALT > 3 × ULN	Normal or elevated	Severe fatigue, nausea, vomiting, right upper quadrant pain	
If elevated at baseline: ALT > 2 × baseline or > 300 U/L (whichever occurs first)			

Table 10-4 Follow-up requirements for liver laboratory triggers - Isolated Hyperbilirubinemia

Criteria	Actions required	Follow-up monitoring
Total Bilirubin (isolated)		
>1.5 – 3.0 ULN	
 Maintain treatment Repeat Liver Function Tests (LFTs) within 48-72 hours 	Monitor LFTs weekly until resolution to ≤ Grade 1 or to baseline
> 3 - 10 × ULN (in the absence of known Gilbert syndrome)	
 Interrupt treatment Repeat LFTs within 48-72 hours Hospitalize if clinically appropriate Establish causality Record the AE and contributing factors (e.g. conmeds, med hx, lab) in the appropriate eCRF 	Monitor LFTs weekly until resolution to ≤ Grade 1 or to baseline (ALT, AST, total bilirubin, Alb, PT/INR, ALP and GGT) Test for hemolysis (e.g. reticulocytes, haptoglobin, unconjugated [indirect] bilirubin)
> 10 × ULN	
 Discontinue the study treatment immediately Hospitalize the participant Establish causality Record the AE and contributing factors(e.g. conmeds, med hx, lab)in the appropriate eCRF 	ALT, AST, total bilirubin, Alb, PT/INR, ALP and GGT until resolution (frequency at investigator discretion)
Any AE potentially indicative of a liver toxicity	
 Consider study treatment interruption or discontinuation Hospitalization if clinically appropriate Establish causality Record the AE and contributing factors(e.g. conmeds, med hx, lab)in the appropriate eCRF 	Investigator discretion

Based on the Investigator's clinical judgement, investigation(s) of the contributing factors for the liver event can include: serology tests, imaging and pathology assessments, hepatologist's consultancy; obtaining more detailed history of symptoms and prior or concurrent diseases, history of concomitant drug use, and/or exclusion of underlying liver disease.

